5.3. Randomization Criteria

Subjects must fulfill the following criteria to be randomized to study treatment:

1. **Diary compliance:** Compliance with completion of the Diary as defined as:
 - a. Completion of questions on 4 or more of the last 7 days immediately prior to Visit 2 (includes the morning of Visit 2).
 - b. **Note:** If the Diary was completed on < 4 days due to technical challenges, the Visit 2 may be delayed up to an additional 3 days to allow for completion of the Diary parameters above.
2. **Eosinophilic Phenotype:** Subjects must meet at least one of the criteria below.
 - Blood eosinophil count ≥ 250 cells/ μ L obtained at Visit 1.
OR
 - Minimum NPS of 4 out of a maximum score of 8 with a score of at least 2 for each nostril as assessed by a blinded central reader. Subjects with an NPS of 1-3 are not eligible for randomization.
3. **CRS exacerbation:** Subjects who experience a CRS exacerbation during the Run-in period should have their Randomization Visit (Visit 2) delayed until the investigator considers the subject has returned to their baseline status. If a 4-week Run-in period has elapsed before the subject is back to baseline status, then the subject will be considered a Run-in failure. CRS exacerbation is defined in [Section 8.1.6](#).
4. **Laboratory abnormality:** No evidence of clinically significant abnormality in the hematological, biochemical, or urinalysis at Screening visit, as judged by the investigator.
5. **Hepatitis status:** No diagnosis of chronic hepatitis B or C, as evidenced by a negative hepatitis B surface antigen (HBsAg) or hepatitis C antibody screen at Screening visit.
6. **Chemistry and hematology obtained at Screening visit:**
 - ALT $\leq 1 \times$ the upper limit of normal (ULN)
 - AST $\leq 1 \times$ ULN
 - Alkaline phosphatase $< 2 \times$ ULN
 - Bilirubin $< 1 \times$ ULN
 - Absolute eosinophil count $< 1,500$ cells/ μ L
 - White blood cell count $< 15,000$ cells/ μ L
7. **Pregnancy test:** For WOCBP, both the serum pregnancy test at the Screening visit and the urine pregnancy test at Visit 2 must be negative.
8. **Use of MFNS:** Subject newly switched onto MFNS during screening should tolerate MFNS during Run-in.
9. **Nasal symptoms:** SNOT-22 score ≥ 17 as assessed at randomization.
10. **ECG overread:** ECG overread by the central ECG reader confirms the QTcF interval is < 450 msec for males or QTcF < 470 msec for females.

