9.4.1.2. Secondary Efficacy Analysis

The secondary endpoints of change from baseline to Week 16 in Lund-Mackay total score and in UPSIT score will be analyzed utilizing analysis of covariance (ANCOVA) models including covariates for baseline score, presence or absence of bilateral NP, and treatment group. Results will be presented in terms of least squares mean differences, along with corresponding 95% CIs and p-values.

The secondary endpoints of change from baseline to Week 16 in NPS, NC, and TSS will be analyzed with MMRM using an REML approach, employing a similar methodological approach as the analysis of the primary endpoint. The analysis of change from baseline to Week 16 in NPS will be conducted in the CRSwNP stratum, with the fixed, categorical effect for randomization strata in the MMRM model defined by presence of NP and comorbid asthma (ie, CRSwNP with comorbid asthma and CRSwNP without comorbid asthma). For NC and TSS, the average of the scores recorded during the last 7 days before a given visit (14 scores, including the morning of the visit) will be used to determine the value for that visit.

The secondary endpoint of time to first response (≥ 1 point improvement from baseline) in NPS will be conducted in the CRSwNP stratum and will be analyzed using a stratified Cox proportional hazards model, stratified on the basis of the presence or absence of comorbid asthma, adjusted for country, baseline NPS, and treatment group. Subjects without a response in NPS will be censored at their last NPS assessment. The secondary endpoint of time to first CRS exacerbation will be analyzed using a stratified Cox proportional hazards model, stratified on the basis of the presence or absence of NP and comorbid asthma (ie, CRSwNP with comorbid asthma, CRSwNP without comorbid asthma, and CRSsNP), adjusted for country and treatment group. Subjects without a CRS exacerbation will be censored at their last assessment for CRS exacerbation. Kaplan-Meier estimates and curves will be provided for both time to first response in NPS and time to first CRS exacerbation.

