8.3.1.2. MMRM with MI

Missing SNOT-22 total scores at post-baseline visits will be imputed using an MI approach. Missing SNOT-22 total scores at baseline will not be imputed.

The following steps will be performed:

- Step 1: Intermittent missing values will be imputed using the Markov Chain Monte Carlo (MCMC) method ([Schafer, 1997](#)), using a noninformative prior (Jeffreys) for the prior information for the means and covariances and expectation-maximization (EM) for the initial mean and covariance estimates.
- Step 2: Monotone missing values will then be imputed using a linear regression model ([Allison, 2005](#)) including the imputed intermittent missing values in step 1. A monotone missing pattern is such that in the event that a variable is missing it is implied that all subsequent variables are also missing (e.g., once a subject withdraws from study, no additional data is expected for that subject).
- For each step, MI will be performed within each treatment group with covariates for disease status stratification factor values used for randomization (CRSwNP with

comorbid asthma, CRSwNP without comorbid asthma, and CRSsNP), region (United States, Eastern Europe), and non-missing values for baseline SNOT-22 total score and Weeks 4, 8, 12, and 16 SNOT-22 total scores. Should convergence issues occur due to small cell size for the categorical covariates at either step, the categorical variable(s) causing convergence issues will be removed from the model.

- Missing change from baseline and percent change from baseline in SNOT-22 total scores will be computed from the imputed SNOT-22 total scores.
- The analysis of the primary endpoint as described in [Section 8.3.1](#) will be performed for each complete, imputed dataset.
- For step 1, fifty imputations will be performed. For step 2, 1 imputation will be performed if 50 imputations were performed for step 1. Fifty imputations will be performed for step 2 if step 1 was skipped (e.g., for assessments only collected once post-baseline or for endpoints without intermittent missing values).
- Results of the MMRM on the multiple imputed data sets will be combined to generate an overall estimate and associated variance using Rubin's rules ([Rubin, 1987](#)).

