8.3.2.2. Time to Event Endpoints

Time to first response in NPS is defined as the time from the date of the first dose of study treatment to the first date with ≥ 1 point improvement in NPS from baseline for subjects in the randomized CRSwNP stratum. Subjects in the randomized CRSwNP stratum who do not experience ≥ 1 point improvement in NPS from baseline will be censored at their last post-baseline NPS assessment, or on Day 1 if no baseline NPS assessment or no post-baseline NPS assessment was performed.

CRS exacerbation is defined as deterioration of CRS symptoms requiring treatment with an antibiotic, an anti-inflammatory drug, or a symptom reliever; an Emergency Department visit; or hospitalization (Kuiper, 2018). Time to first CRS exacerbation is defined as the time from the date of the first dose of study treatment to the first date of treatment with an antibiotic, an anti-inflammatory drug, or a symptom reliever, the date of Emergency Department visit, or the date of hospitalization, whichever occurs first. Subjects without a CRS exacerbation will be censored at their last post-baseline CRS exacerbation assessment, or on Day 1 if no post-baseline CRS exacerbation assessment was performed.

For the primary analysis of both time to event endpoints, all data through Week 16 will be included; a sensitivity analysis of both time to event endpoints will be performed including all data.

The number and proportion of subjects with a response in NPS will be summarized for subjects in the randomized CRSwNP stratum. Time to first response in NPS will be compared between treatment groups using a Cox proportional hazards model and will include covariates for treatment group, disease status stratification factor values used for randomization (CRSwNP with comorbid asthma, CRSwNP without comorbid asthma, and CRSsNP), region (United States, Eastern Europe), and baseline NPS.

The number and proportion of subjects with CRS exacerbations will be summarized. Time to first CRS exacerbation will be analyzed using a Cox proportional hazards model and will include covariates for treatment group, disease status stratification factor values used for randomization (CRSwNP with comorbid asthma, CRSwNP without comorbid asthma, and CRSsNP), and region (United States, Eastern Europe).

The exact method will be used to handle ties in event times.

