8.3.3.3. Annualized Rate of CRS Exacerbations

The date of onset of a CRS exacerbation will be considered to be the first date of treatment with an antibiotic, an anti-inflammatory drug, or a symptom reliever, the date of Emergency Department visit, or the date of hospitalization, whichever occurs first. The end date of a CRS exacerbation will be considered to be the last date of treatment with an antibiotic, an anti-inflammatory drug, or a symptom reliever, or 6 days after the date of onset (for a total duration of 7 days), whichever is later. Courses of treatment separated by 7 or more days will be counted as separate exacerbations.

The number and proportion of subjects with 0, 1, and ≥ 2 CRS exacerbations and the adjusted annualized rate of CRS exacerbations will be summarized by treatment group. The unadjusted annualized rate of CRS exacerbations will be calculated as the total number of CRS exacerbations divided by the total number of subject-years of follow-up and will also be summarized by treatment group.

The total number of CRS exacerbations will be analyzed using a negative binomial regression model, with the logarithmic transformation of follow-up time as the offset parameter. The follow-up time is defined as the subject's time on study through Day 120. The model will include terms for treatment group, disease status stratification factor values used for randomization (CRSwNP with comorbid asthma, CRSwNP without comorbid asthma, and CRSsNP), and region (United States, Eastern Europe). If the distribution of CRS exacerbation data is underdispersed, or if the negative binomial regression model fails to converge, a Poisson regression model will be used instead of the negative binomial regression model.

The rate ratio for the GB001 40 mg group versus placebo, corresponding 95% CI, and p-value will be provided from the model. The percentage reduction and corresponding 95% CI will also be provided.

Lastly, the subject CRS exacerbation rate will be calculated as the number of CRS exacerbations for each subject divided by the number of years followed in the study for that subject and will be summarized by treatment group.

Analyses of annualized rate of CRS exacerbations may also be presented by various time periods (Baseline through Week 8, Week 8 through Week 16, and Baseline through Week 20 [Follow-up]) in order to elucidate onset and durability of effect over time.

CRS exacerbation data will also be presented in by-subject data listings.

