8.3.3.4. Proportion of Subjects with Antibiotic Use Due to Worsening CRS by Week 16

The proportion of subjects with antibiotic use due to worsening of CRS by Week 16 will be analyzed using a logistic regression model to compare the GB001 40 mg group with placebo, using the approach described in [Section 8.3.1.5](#), excluding baseline SNOT-22 total score as a covariate in the model.

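### The exacerbation and antibiotic-use models omit baseline SNOT-22; adding it is a cheap improvement, but its gain depends on a prognostic link the documents do not give

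*SAP*

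**What the plan says.** Three models are concerned.

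- Time to first CRS exacerbation (secondary, SAP 8.3.2.2): "Time to first CRS exacerbation will be analyzed using a Cox proportional hazards model and will include covariates for treatment group". The remaining covariates are the three-level disease stratum used at randomization and region.
- Annualized exacerbation rate (exploratory, SAP 8.3.3.3), negative binomial: "The model will include terms for treatment group, disease status stratification factor values used for randomization", plus region, with log follow-up time as offset.
- Antibiotic use for worsening CRS by Week 16 (exploratory, SAP 8.3.3.4), logistic: the approach of SAP 8.3.1.5, "excluding baseline SNOT-22 total score as a covariate in the model".

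Protocol 9.4.1.2 also leaves SNOT-22 out of the exacerbation Cox model, which is stratified on polyp and asthma status and "adjusted for country and treatment group". By contrast, the Cox model for NPS response in SAP 8.3.2.2 ends its covariate list with "region (United States, Eastern Europe), and baseline NPS".

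On availability, Protocol 5.3 criterion 9 requires "SNOT-22 score ≥ 17 as assessed at randomization", and exclusion criterion 1 in Protocol 5.2 needs a screening score as well. SAP 3 takes the last non-missing pre-dose value as baseline. SAP 8.3.1.2 still allows for a gap: "Missing SNOT-22 total scores at baseline will not be imputed".

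Power is stated only for SNOT-22 and NPS (SAP 2.5, Protocol 9.2). No event rate, hazard ratio or power is given for any exacerbation or antibiotic-use endpoint.

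**The concern.** An exacerbation here is a worsening of CRS symptoms that leads to treatment, and a symptom reliever is enough to qualify. Symptom burden at baseline is an obvious candidate predictor of such events, and it is measured before the first dose. In Cox and logistic models, leaving out a prognostic covariate pulls the estimated treatment effect toward the null and costs power. With about 50 subjects per arm followed for 16 weeks, events may be few, so any loss falls on a comparison that is already weak.

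SNOT-22 is also not a stratification factor, so chance imbalance between arms is left uncontrolled in these three analyses. If the score is prognostic, an imbalance would invite a post hoc argument that pre-specified adjustment avoids.

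**Working it through.** **1. The plan's own figures.** After 15% dropout, 50 per arm becomes 50 × 0.85 = 42.5, and 32 becomes 27.2. The noncentrality is Δ / (SD × √(2/n)).
- SNOT-22: 12.0 / (16.8 × √(2/42.5)) = 3.29; two-sided t-test power 0.902 (stated: about 90%).
- NPS: 1.3 / (1.7 × √(2/27.2)) = 2.82; power 0.791 (stated: about 80%).

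Both reproduce. Neither concerns the exacerbation endpoints.

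**2. Event count is the main limit.** With 1:1 allocation, Schoenfeld's formula gives events = 4(z₀.₉₇₅ + z₀.₈₀)² / (ln HR)².
- 80% power at HR 0.5: 4 × (1.960 + 0.842)² / 0.693² ≈ 65.4, so 66 events. At HR 0.6: 121 events.
- With 30 events at HR 0.5: z = 0.693 × √(30/4) − 1.960 = −0.06, power 0.475.

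**3. Cox power with and without baseline SNOT-22.** Assumptions, none of them from the documents: treatment HR 0.5, the placebo risks shown, the HR per SD of baseline shown, and the stratum-by-region mix. From the documents: N = 100, 1:1, 16 weeks, two-sided 0.050. The 15% dropout is borrowed from the primary endpoint. Both models contain treatment, three strata and region; 3000 trials per cell, so simulation error on each power is about 1 point.

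| Placebo 16-week risk (mean events) | HR per SD 1.0 | 1.25 | 1.5 | 2.0 |
|---|---|---|---|---|
| 20% (about 14) | 0.214 → 0.223 | 0.194 → 0.205 | 0.205 → 0.223 | 0.200 → 0.228 |
| 40% (about 29) | 0.460 → 0.460 | 0.437 → 0.439 | 0.428 → 0.457 | 0.395 → 0.447 |
| 60% (about 46) | 0.644 → 0.640 | 0.645 → 0.647 | 0.609 → 0.651 | 0.550 → 0.650 |

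The changes are −0.4 to +0.9 points with no prognostic value, +0.2 to +1.1 at 1.25, +1.8 to +4.2 at 1.5, and +2.8 to +10.0 at 2.0. The −0.4 is within simulation error. A second simulation of the same model, indexed by log-HR per SD, gave about 0 to 1 point at 0, 1 to 3 at 0.3, 1 to 6 at 0.5 and 3 to 11 at 0.7. A log-HR of 0.7 is a hazard ratio of exp(0.7) ≈ 2.0.

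**4. Type I error, Cox table.** Without the covariate 0.046 to 0.057; with it 0.046 to 0.063. The highest pair, in one cell, is 0.057 without and 0.063 with.

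**5. Logistic model** (assumed OR 0.4; 3000 trials per cell). At 15% placebo risk: 0.198 → 0.207 with no prognostic value, 0.185 → 0.205 at OR 2.0 per SD. At 30%: 0.462 → 0.468 and 0.417 → 0.440. Over all completed cells the gain was 0.5 to 2.3 points. Type I error with the covariate was 0.040 to 0.054. Higher risks were not completed.

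**6. Negative binomial model** (assumed rate ratio 0.5, dispersion 0.5; 1000 trials per cell). The change was −1.3 to +1.1 points, which is noise. The log-link rate ratio is collapsible, so the attenuation argument does not carry over. Strong covariates at the higher event rates were not completed.

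**7. Chance imbalance.** The SE of the between-arm difference in standardized baseline is √(2/50) = 0.20, a 95% range of ±0.39 SD. At an assumed log-HR of 0.5 per SD, that shifts the unadjusted HR by a factor of exp(±0.196), or 0.82 to 1.22.

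**The case against.** The omission follows a rule. The SAP adjusts for the baseline of the endpoint itself: NPS for NPS response, SNOT-22 for SNOT-22 response. Exacerbations and antibiotic courses have no such score. A reader might see the NPS Cox model as an inconsistent precedent, but it is adjusting for its own outcome. A reader might also take the wording in SAP 8.3.3.4 as a deliberate rejection of a known predictor. It more plausibly just removes a term that belongs to the borrowed SNOT-22 responder model, leaving the same terms as the other two models. Both objections stand, and the protocol's Cox model has the same omission.

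Nor do the documents say that SNOT-22 predicts exacerbation. A high but stable score need not foretell deterioration. That stands too, and it makes any gain conditional.

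The covariate is not costless. The Cox model already has four parameters (one treatment, two stratum, one region). At about 14 events, a fifth takes events per parameter from 14/4 = 3.5 to 14/5 = 2.8. A subject with no baseline score would drop out of the analysis, and SAP 5.1 provides for subjects randomized in error, so universal availability cannot be assumed. In practice the score is missing only if both the screening and the randomization values are. The hazard and odds ratios become conditional on baseline severity, although the planned ones are already conditional on stratum and region.

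What remains is an asymmetry for the Cox and logistic models: some gain if the score is prognostic, and close to nothing lost if it is not.

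**Conclusion.** A minor, optional improvement. All three models omit a pre-dose severity score that correctly randomized subjects have, and no reason is given. It is neither an error nor a departure from the protocol.

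A reader might infer that power is being given away for nothing. The documents do not support that: they give no link between SNOT-22 and exacerbation and no event rate. Under the assumed inputs the Cox gain is about 0 to 1 point if the score is not prognostic, 1 to 6 points at log-HR 0.3 to 0.5 per SD, and 3 to 11 at 0.7. The largest gains need both a hazard ratio near 2 per SD and a placebo risk of 60%. Even there, tabulated power reaches only 0.65 at HR 0.5, because events are the limit. The logistic gain was 0.5 to 2.3 points in the cells completed, and no benefit was shown for the negative binomial model. One endpoint is secondary and two are exploratory, and none has a power target.

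**What to change.** Before unblinding, amend the SAP to add baseline SNOT-22 total score as a continuous covariate:

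- in the Cox model for time to first CRS exacerbation (8.3.2.2);
- in the antibiotic-use logistic model (8.3.3.4), by deleting the clause that excludes it;
- in the negative binomial model (8.3.3.3), for consistency, accepting that the benefit there is less certain.

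List the Cox change as a change from Protocol 9.4.1.2, which names that model's covariates. State how a subject without a baseline score is handled, and report the hazard and odds ratios as conditional on baseline severity. If the sponsor prefers to keep the planned models as primary, pre-specify the adjusted versions as sensitivity analyses, or give the reason for leaving the score out.

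The cost is SAP wording, one extra parameter per model, and the loss of any subject without a baseline score. No new data are needed. If the change is made only after unblinding, SAP 1 would have it labelled post hoc, and most of its value is gone.

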8.3.3. Exploratory and Additional Analyses

The exploratory and additional endpoints are listed in [Table 1](#) and will be analyzed as described below.

8.3.3.1. Change from Baseline to Week 16 Endpoints

The VAS for rhinosinusitis is used to evaluate the total severity and is only validated in adult CRS to date ([Fokkens, 2007](#)). The subject is asked to indicate on a VAS the answer to the question: “How troublesome are your symptoms of rhinosinusitis?” The VAS ranks from 0 (Not troublesome) to 10 (Worst thinkable troublesome) (as defined in [Protocol Section 10.7](#)). The disease can be divided into Mild, Moderate, and Severe based on total severity VAS score (0 to 10 cm):

- Mild = VAS 0-3
- Moderate = VAS > 3-7
- Severe = VAS > 7-10

Percentage of maxillary sinus volume occupied by disease on CT scan, volume of the air (mL), volume of mucosa (mL), and thickness of lateral wall (mm) will be calculated each for the left and right sides and averaged for analysis, using the non-missing values at each visit.

Change from baseline to Week 16 in VAS score and percentage of maxillary sinus volume occupied by disease on CT scan, volume of the air, volume of mucosa, and thickness of lateral wall will be analyzed using ANCOVA models without MI. The ANCOVA models will be analogous to those described in [Section 8.3.1.3](#), with the baseline value specific to each endpoint included as a covariate. The models will include covariates for treatment group, disease status stratification factor values used for randomization (CRSwNP with comorbid asthma, CRSwNP without comorbid asthma, and CRSsNP), region (United States, Eastern Europe), and baseline value. LS means, SEs, and corresponding 95% CIs for each treatment group, and differences in LS means, SEs, corresponding 95% CIs, and p-values for the GB001 40 mg group versus placebo will be provided.

Actual values and change from baseline values in VAS scores will be descriptively summarized by visit using as observed data.

VAS score, percentage of maxillary sinus volume occupied by disease on CT scan, volume of the air, volume of mucosa, and thickness of lateral wall data will be presented in by-subject data listings.

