8.1.2. Computer Tomography (CT)

CT of the sinuses will be performed at Randomization, at end of treatment (Visit 7) and if a patient is withdrawn early.

For the accurate assessment of Lund-Mackay scores and 3D volumetric measurement of the maxillary sinus, the same acquisitions (sequences) will be performed and used for centralized imaging data assessments and scored by the imaging core laboratory.

Blinded central reading of the Visit 2 assessment will be used for comparison with the Week 16 visit. The final results of blinded central reading will be made available after the study.

Details on CT will be available in a separate operational manual provided to the sites.

The Lund-Mackay system is based on localization with points given for degree of opacification: 0 = normal, 1 = partial opacification, 2 = total opacification. These points are then applied to the maxillary, anterior ethmoid, posterior ethmoid, sphenoid, frontal sinus on each side. The osteomeatal complex is graded as 0 = not occluded, or 2 = occluded deriving a maximum score of 12 per side ([Lund, 1993](#)). This scoring system has been validated in several studies ([Scadding, 2011](#); [Hopkins, 2009](#)).

For subjects in whom the osteomeatal complex (OC) is missing (because of a previous surgery) the blinded central reader should consider the location of the former OC and provide a scoring (as if the OC was there).

Three-Dimensional volumetric measurement of the maxillary sinus will be performed at the imaging core laboratory.

This method is used to calculate:

- volume of the air (mL)
- volume of mucosa (mL)
- percent occupied by disease
- thickness of lateral wall

For the analysis, blinded central reading of the CT at Visit 2 will be used for comparison with Week 16. The sites will remove subject-identifying information from the imaging data header prior to sending the imaging data to the imaging core laboratory. The percent change in opacification from baseline to end of treatment will be calculated ([Van Agthoven, 2001](#)).

If a prior CT within 60 days of the Randomization visit is available and the Imaging Core Laboratory confirms their quality criteria are met, this CT may be acceptable.

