• To evaluate the effect of GB001 on CRS exacerbation rate	• Annualized rate of CRS exacerbations
• To evaluate the effect of GB001 on maxillary CT opacification	• Change from baseline to Week 16 in percentage of maxillary sinus volume occupied by disease on CT scan
• To evaluate the effect of GB001 on worsening of CRS requiring the use of antibiotics	• Proportion of subjects with antibiotic use due to worsening CRS by Week 16
• To evaluate PK of GB001	• Plasma concentration of GB001
• To evaluate the effect of intervention on, as a function of, the PD markers	• Correlation between baseline markers and safety, tolerability, and efficacy parameters • Change in PD markers over time
• To evaluate the relationship between safety, efficacy, and exposure parameters and pharmacogenetics (PGx)	• Correlation between baseline characteristics and single nucleotide polymorphisms • Change from baseline in safety, efficacy, and exposure parameters as a function of single nucleotide polymorphisms

Additional efficacy endpoints not defined in the protocol but defined in this SAP include:

- Proportion of subjects with a ≥ 9 point decrease from baseline at Week 16 in SNOT-22 total score
- Proportion of subjects with a reduction from baseline of ≥ 1 in NPS at Weeks 8 and 16
- Change from baseline to Week 16 in anterior rhinorrhea, posterior rhinorrhea, and loss of sense of smell scores
- Change from baseline to Week 16 in volume of the air, volume of mucosa, and thickness of lateral wall
- Change from baseline to Week 16 in Asthma Control Questionnaire (ACQ-5) score.

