3.2. Standard Calculations

Standard calculations are described as follows:

Age:

If age is not collected on the electronic case report form (eCRF), age at screening will be calculated in years using the date of birth and the date of the Screening visit (Visit 1), rounded down to the nearest integer.

Duration:

Duration between two dates date1 and date2 will be calculated as follows:

date2 – date1 + 1, when expressed in days

(date2 – date1 + 1)/7, when expressed in weeks

(date2 – date1 + 1)/365.25, when expressed in years

Change/Percent Change from Baseline:

Change from baseline will be calculated as: Value at post-baseline visit – value at baseline

Percent change from baseline will be calculated as: (Change from baseline/value at baseline) * 100%

Note: Change from baseline summaries will only include subjects with a baseline value and at least one post-baseline value. If the value at baseline is 0, percent change from baseline will be missing.

Study Day:

Study day will be calculated as follows:

assessment date – date of the first dose of study treatment, where assessment date < date of the first dose of study treatment

assessment date – date of the first dose of study treatment + 1, where assessment date \geq date of the first dose of study treatment

Date Imputation:

If complete dates are unavailable, July 2 (midpoint of a non-leap year) will be utilized in calculations in cases where both month and day are missing, and the 15th will be utilized in calculations in cases where only day is missing.

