8.3.3.5. Other Endpoints

8.3.3.5.1. Nitric Oxide

Nitric oxide will be measured both by oral (FeNO) and nasal (nasal nitric oxide [nNO]) methods. nNO data will be analyzed for the same nostril, either left or right, per subject at all visits. The primary nNO analysis will include subjects with a change from baseline to Week 16 value for a single nostril and subjects with change from baseline to Week 16 values for both nostrils where the nostril with the lower (i.e., worse) value at baseline is used. In the case of ties at baseline, the nostril with the lower (i.e., worse) change from baseline at Week 16 will be selected for summary. A sensitivity nNO analysis will include subjects with a change from baseline to Week 16 value for a single nostril and subjects with change from baseline to Week 16 values for both nostrils where the nostril with the higher (i.e., better) value at baseline is used. In the case of ties at baseline, the nostril with the higher (i.e., better) change from baseline at Week 16 will be selected for summary.

Change from baseline to Week 16 in both FeNO and nNO and percent change from baseline to Week 16 in both FeNO and nNO will be analyzed using ANCOVA models without imputation. LS means, SEs, and corresponding 95% CIs for each treatment group, and differences in LS means, SEs, corresponding 95% CIs, and p-values for the GB001 40 mg group versus placebo will be provided. The models will include covariates for treatment group and baseline FeNO or nNO. Analyses may be conducted using log transformed data in the case of non-normality.

Actual, change from baseline, and percent change from baseline values in FeNO and nNO will be descriptively summarized by visit using as observed data.

Nitric oxide data will also be presented in a by-subject data listing.

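### SAP 8.3.3.1 averages the maxillary CT measures over whichever sides are readable at each visit, so a side missing at only one visit puts half the left-right difference into the change score

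*SAP*

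**What the plan says.** SAP 8.3.3.1 covers four maxillary sinus measures from CT: percentage of volume occupied by disease, air volume, mucosal volume and lateral wall thickness. They "will be calculated each for the left and right sides and averaged for analysis, using the non-missing values at each visit". The sides that enter the average are therefore decided separately at each visit. SAP 3.2 gives the general rule for change: "Change from baseline will be calculated as: Value at post-baseline visit – value at baseline". Together, these make the outcome a difference of two separately formed averages.

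SAP 2.1 lists one of these endpoints as exploratory ("Change from baseline to Week 16 in percentage of maxillary sinus volume occupied by disease on CT scan") and the others among the efficacy endpoints added by the SAP ("Change from baseline to Week 16 in volume of the air, volume of mucosa, and thickness of lateral wall"). On the analysis, SAP 8.3.3.1 says that VAS, percent occupied, "volume of the air, volume of mucosa, and thickness of lateral wall will be analyzed using ANCOVA models without MI". SAP Table 1 shows that single analysis for them and no sensitivity analysis.

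On timing, protocol 8.1.2 says: "CT of the sinuses will be performed at Randomization, at end of treatment (Visit 7) and if a patient is withdrawn early". The planned comparison thus rests on one baseline scan and one post-baseline scan.

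For nasal nitric oxide, another two-sided measure, SAP 8.3.3.5.1 holds the side constant: "nNO data will be analyzed for the same nostril, either left or right, per subject at all visits".

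**The concern.** A change score should compare the same anatomy at two times. Under the CT rule it may not. If both sides are read at baseline and one at Week 16, or the reverse, part of the computed change is the standing difference between the two sides. For the volumes in mL, that difference includes ordinary asymmetry in sinus size as well as asymmetry of disease.

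The affected subject enters the ANCOVA as fully observed, because the average exists at both visits. Nothing in the SAP flags the subject, sets the value to missing, or repeats the analysis in subjects with both sides at both visits. At stake are the precision of the exploratory and additional CT results and, under a narrower condition set out below, their freedom from bias.

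**Working it through.** The plan states no figure for this point, so there is none to reproduce. The check is algebra, followed by a simulation to judge size.

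**1. The artefact.** Let L0, R0 be the baseline values and L16, R16 the Week 16 values.

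- Both sides at baseline, right only at Week 16: change = R16 − (L0 + R0)/2 = (R16 − R0) + (R0 − L0)/2.
- Right only at baseline, both at Week 16: change = (L16 + R16)/2 − R0 = (R16 − R0) + (L16 − R16)/2.
- Left only at baseline, right only at Week 16: change = R16 − L0 = (R16 − R0) + (R0 − L0).

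The last term in each line is the artefact: half the left-right difference in the first two cases and all of it in the third. It is zero if the sides are equal or if the same side is missing at both visits.

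**2. Examples (assumed values, percent occupied, no true change).**

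| Left / right | Left missing at Week 16 | Right missing at Week 16 | Left only at baseline, right only at Week 16 |
|---|---|---|---|
| 50 / 50 | 0 | 0 | 0 |
| 40 / 60 | +10 | −10 | +20 |
| 20 / 80 | +30 | −30 | +60 |

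Using only sides measured at both visits gives 0 in the first two cases and a missing change in the third.

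**3. Spread of the artefact.** With per-side SD s and left-right correlation r, the artefact from losing one side at one visit has SD s × √(2(1 − r))/2. With s = 30 and r = 0.5 (assumed), this is 30 × √1/2 = 15 points per affected subject.

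**4. Effect on the treatment estimate.** The simulation used 42 subjects per arm (50 × 0.85 = 42.5, from the planned size and 15% dropout in protocol 9.2). Assumed inputs: side SD 25, change SD 15, no treatment effect, one randomly chosen side missing at one randomly chosen visit, and ANCOVA on baseline and treatment, with 1,500 repetitions per setting. Entries are the variance of the treatment estimate under the SAP rule divided by that under the same-side rule.

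| Left-right correlation | 5% affected | 10% affected | 20% affected | Artefact SD (s = 25) |
|---|---|---|---|---|
| 0.3 | 1.046 | 1.131 | 1.148 | 14.8 |
| 0.6 | 1.047 | 1.052 | 1.106 | 11.2 |
| 0.9 | 1.008 | 0.999 | 1.013 | 5.6 |

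The range is about 0% to 15% more variance. The largest ratio corresponds to a standard error √1.148 = 1.071 times as large. The value just below 1 is simulation error. Mean treatment estimates under the SAP rule lay within 0.16 points of zero. The furthest, −0.155, has a simulation standard error of 2.979/√1500 = 0.077, and the same-side rule gave −0.119 on the same data. There is no sign of systematic bias.

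**5. When bias would arise.** Before covariate adjustment, the bias in the treatment difference is p_G × m_G − p_P × m_P. Here p is the proportion affected in each arm (GB001, placebo) and m is the mean artefact among those affected. If the lost side is as likely to be the better as the worse one, m is zero in both arms and the bias is zero even when p_G and p_P differ. Bias needs a non-zero m and a product p × m that differs between arms.

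**The case against.** The strongest reply is that the trigger may never occur. One CT images both sides. Protocol 8.1.2 calls for the same acquisitions and central scoring, and a historic baseline scan is used only if "the Imaging Core Laboratory confirms their quality criteria are met, this CT may be acceptable". A lasting cause of unreadability would affect the same side at both visits, where the artefact is zero. The endpoints are exploratory or additional. Summing or averaging the available components is also the SAP's convention for SNOT-22 (8.3.1) and ACQ-5 (8.3.3.5.2).

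Much of this stands. It limits the size of the problem and leaves its frequency unknown. It does not remove the flaw, because the wording about non-missing values has a function only if a side can be missing. The stated quality check concerns a historic scan and does not require the same sides to be measurable at Week 16.

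A reader might also infer more than the documents support:

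- *That the change generally compares different sinuses.* With one side missing at one visit, it compares a two-side mean with one of those same two sides. Wholly different sinuses are compared only when opposite sides are missing at the two visits.
- *That more side loss in one arm is enough for bias.* Step 5 shows that unequal loss alone adds noise. A side that is altered but still readable is not missing, so this rule does not act on it.
- *That the SAP contradicts itself.* The nNO rule selects one nostril and does not average two. It shows that the SAP holds the side fixed elsewhere, but it is not a conflicting instruction for CT.

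**Conclusion.** The point holds as a minor flaw in a derivation rule. The per-visit averaging follows directly from the text, the artefact is exact algebra, and neither document contains a provision that prevents it.

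Its size in this trial cannot be stated, because the documents give neither the number of subjects with a side missing at one visit only nor the degree of left-right asymmetry. If there are no such subjects, the effect is nil. The range of about 0% to 15% more variance rests on the assumed SDs and correlations, 5% to 20% of subjects affected, and loss unrelated to disease or arm. A bias is possible only under the condition in step 5, and nothing in the documents indicates that it is met.

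The primary SNOT-22 analysis and the secondary Lund-Mackay score do not use this rule. The improvement is worth making because it is cheap, not because a main conclusion depends on it.

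**What to change.** In SAP 8.3.3.1, replace the averaging rule for the four CT measures:

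- compute the change for each side measured at both baseline and Week 16, and average those side-specific changes;
- take the baseline covariate from the same side or sides;
- set the change to missing if no side is common to both visits;
- report by arm how many subjects had a side missing at one visit only.

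The cost is a sentence or two in the SAP and minor programming. There is a small loss: a side observed at only one visit is not used, and a subject with no common side drops out of these analyses. If the SAP can no longer be amended before unblinding, SAP section 1 allows the same-side analysis to be added and identified in the study report as post hoc.
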